9.1.4 Withdrawals and Deviations

All withdrawn subjects will be listed individually, including at least subject number, date and reason for withdrawal, and last visit performed.

9.2 Sample Size Determination

The study is planned to include approximately 400 subjects; 80 will be treated in each dose group. [REDACTED]

Effective date: 2018-08-10 13:08

Effective

Version: 1.0

Thus, a sample size of 80 in each group is planned to be sufficient to explore the safety and responder rates over time.

9.2.4 Interim Analysis

10 TRAINING / MONITORING / DATA MANAGEMENT / QUALITY ASSURANCE

10.1 Personnel Training

Investigators and other responsible persons should be listed together with their function on the study on the signature and delegation log. Study staff shall provide a curriculum vitae or equivalent, as appropriate.

It is the responsibility of the PI to ensure that all personnel involved in the study are fully informed of all relevant aspects of the study, including detailed knowledge of and documented training in all procedures to be followed.

10.2 Clinical Monitoring

The conduct of the clinical study will be closely monitored by representatives of the Sponsor to verify adherence to the clinical study protocol, ICH-GCP guidelines, and applicable SOPs.

The Investigator will allow the CRO/Sponsor's representatives, to have direct access to all clinical study records, CRFs, corresponding subject medical records, study product(s) dispensing records, and any other documents considered source documentation. Additionally, the CRO/Sponsor representative is to have access to the study product storage area and clinical study facilities.

The Investigator also agrees to assist the representative if required.

10.3 Data Management

All data management procedures will be detailed in a Data Management Plan (DMP).

The DMP will describe the Clinical Data Management System (CDMS) that will be used to collect data (either EDC or paper CRF), and whether the data management activities are performed internally or outsourced. Computerized edit checks and review processes will be performed on an ongoing basis as outlined in the DMP until all data clarifications are resolved. The data will be exported to be stored in SAS datasets. After all data clarifications are resolved, coding is approved, SAE/pregnancy reconciliation has been completed (if applicable) and subject's evaluability is determined, the database will be locked.

10.4 Quality Assurance/Audit/Inspection

The clinical study is conducted under the sponsorship of the Sponsor in compliance with the applicable international and local regulatory requirements as well as applicable ICH guidelines and in accordance with the SOPs for clinical study conduct and monitoring from the Sponsor and/or the Contract Research Organization (CRO).

Audits of clinical study centers may be conducted by the Sponsor/CRO representatives, and inspection may be performed by Regulatory Authority inspectorates or IRBs/IECs before, during, or after the clinical study.

The Investigator will allow and assist the CRO/Sponsor's representatives, IRBs/IECs and any regulatory agency to have direct access to all requested clinical study-related records.

For the audits performed by, or on behalf of, the Sponsor auditors, audit certificate(s) will be provided by Quality Assurance.

10.5 [REDACTED]

[REDACTED] [REDACTED]

[REDACTED]

[REDACTED]

[REDACTED]

[REDACTED]

[REDACTED]

[REDACTED]

11 ETHICS AND GENERAL CLINICAL STUDY CONDUCT CONSIDERATIONS

11.1 Independent Ethics Committee (IEC) or Institutional Review Board (IRB)

This clinical study protocol and all amendments will be reviewed and approved by the appropriate IECs/IRBs.

11.2 Ethical Conduct of the Clinical Study

This clinical study will be conducted in accordance with the protocol, the HELSINKI declaration (1964) and subsequent amendments, and the ICH GCP, and in compliance with applicable regulatory requirements.

11.3 Subject Information and Consent

All subjects who participate in this clinical study are required to be fully informed about the clinical study in accordance with GCPs guidelines, federal regulations, HIPAA, and guidelines and in accordance with local requirements.

The ICF (inclusive of HIPPA and photo consent), approved by an IRB/IEC, will be fully explained to the subject. The subject must agree to photo consent in order to participate in the clinical study.

Prior to enrollment into the clinical study, the subject and the PI or designee must sign and date the consent form(s). The Investigator is responsible for maintaining each subject's consent form(s) in the Investigator's site file and providing each subject with a copy of the signed and dated consent form(s).

11.4 Protection of Personal Data

The completion of the study involves the gathering and processing of Personal Data as specified in the Regulation (EU) 2016/679 on the protection of individuals with regard to the processing of personal data and on the free movement of such data. For the purposes of the study, Sponsor will be considered the Data Controller, and Principal Investigator and Institution will both be considered Data Processors.

All processing of Personal Data must be carried out in accordance with national legislation concerning the protection of Personal Data. The Institution and Principal Investigator are responsible for complying with all requirements pursuant to national legislation in the country in which the Institution and Principal Investigator are located.

The Principal Investigator understands that clinical studies conducted under an IND are exempt from the study subject identifier confidentiality provisions of the Health Insurance Portability and Access Act of 1996 (HIPAA), as provided at CFR § 512(b)(iii), and the study subject should be made aware of this exception in the informed consent. The Sponsor shall, to the extent feasible, protect study subject identifier information.

The Institution and Principal Investigator are jointly responsible for obtaining the appropriate informed consent of each subject for the processing of Personal Data required in order to complete the study. Such consent shall include the consent to the transfer of Personal Data to government authorities located in countries outside the US.

The Institution and Principal Investigator are jointly responsible for providing sufficient information to all subjects to enable them to give their informed consent not only to the participation in the study, but also to the processing of Personal Data. Such information includes information regarding the purposes of the processing, the length of time during which Personal Data will be stored, the right of access to stored Personal Data and the right to correction or purging of incorrect or obsolete Personal Data. A subject may also withdraw his or her consent at any time. A subject who withdraws his or her consent to the processing of Personal Data must be considered to have withdrawn from the study but the data collected until the consent was withdrawn may be used in the statistical analyses.

All collection, processing and analyses of protected health information, personal data or similar will be conducted in compliance with applicable local, national and international rules, regulations and guidelines.

11.5 Contractual Requirements

A contractual agreement will be signed between the CRO/Sponsor and each Investigator/Institution. This document will contain supplementary information, including financial terms, confidentiality, the clinical study schedule, third party responsibility, and publication rights.

11.6 Data Collection and Archiving

11.6.1 Data Collection

The Investigator must maintain all required records for all subjects. Data for this clinical study will be recorded in the subject's source documents and in the eCRFs provided by the Sponsor. All data should be recorded in the eCRFs completely and promptly.

11.6.2 Source Documentation

The Investigator must keep accurate separate records (other than the eCRFs) of all subject visits, being sure to include all pertinent clinical study-related information. A statement should be made indicating that the subjects have been included in this clinical study and have provided signed written Informed Consent. All AEs must be thoroughly documented.

Results of any diagnostic tests conducted during the clinical study should also be included in the source documentation.

11.6.3 Archives

All pertinent data, samples, photographs, correspondence, and reports, the original or amended clinical study protocol, and all other material relating to the clinical study will be maintained

securely in Sponsor/CRO/Investigator/Institution archives for the legally required duration for archiving.

The Investigator/Institution should maintain the essential clinical study documents as specified in Section 8 of ICH-GCP, and according to the applicable regulatory requirements.

The Investigator/Institution should take measures to prevent accidental or premature destruction of these documents.

If the Principal Investigator retires, relocates, or withdraws from the responsibility of keeping the clinical study records for any other reasons, custody must be transferred to a person who will accept the responsibility. The Sponsor/CRO must be notified in writing of the name and address of the new custodian.

11.7 Insurance

A certificate attesting Third Party coverage of CRO/Sponsor will be provided upon request.

Effective date: 2018-08-10 13:08

Effective

Version: 1.0

11.9

Effective date: 2018-08-10 13:08

Effective

[figure not shown]
Version: 1.0

[figure not shown]

## 1 Study Information

## 1.1 Background

This statistical analysis plan (SAP) describes the analysis variables and statistical procedures that will be used to analyze and report the results from Protocol 43USD1801 (v1.0), dated 10 AUG 2018.

The SAP was written in accordance with the recommendations outlined in the International Conference on Harmonisation (ICH) E9 Guideline entitled “Guidance for Industry: Statistical Principles for Clinical Trials” and the ICH-E3 Guideline entitled “Guidance for Industry: Structure and Content of Clinical Study Reports”.

### 1.1.1 Study Design

This is a phase 2, multicenter, randomized, dose-ranging, double-blind, placebo-controlled, United States (US) study to assess the safety and efficacy of abobotulinumtoxinA for the treatment of moderate to severe glabellar lines.

After undergoing a screening visit, enrolled subjects will receive a single treatment of abobotulinumtoxinA or placebo at baseline. The planned clinical study duration (from first subject first visit to last subject last visit) is approximately 21.5 months.

### 1.1.2 Number of Subjects and Randomization

The study is planned to enroll approximately 400 subjects who will be treated with [REDACTED] abobotulinumtoxinA (approximately 80 subjects/dose) or placebo (up to 80 subjects depending on the number of dose groups that will run in the study).

Initially, eligible subjects will be randomly assigned at baseline to one of the following treatment

### 1.2.1 Primary Efficacy Objective

The primary efficacy objective is to evaluate a single dose of [REDACTED] abobotulinumtoxinA, respectively, compared to placebo in the treatment of moderate to severe glabellar lines using the Investigator Live Assessment (ILA) [REDACTED] Photographic Scale and the Subject Self-Assessment (SSA) Static [REDACTED] Categorical Scale at maximum frown at Month 1, concurrently.

### 1.2.2 Secondary Efficacy Objectives

- [REDACTED]

### 1.2.3 Safety Objectives

The safety objective is to evaluate the effect on safety endpoints of a single dose of [REDACTED] abobotulinumtoxinA compared to placebo in the treatment of glabellar lines.

## 1.3 Efficacy Assessments

For all assessments, baseline will be defined as the observation that is closest to but prior to study treatment on Day 0. Likewise, change from baseline will be calculated as the value at a given time point minus the baseline value.

- [REDACTED]
- [REDACTED]
- [REDACTED]
- [REDACTED]

## 1.4 Efficacy Endpoints

### 1.4.1 Primary Efficacy Endpoint

The [REDACTED] responder rate will be evaluated using the ILA [REDACTED] Photographic Scale and the SSA Static 4-Point Categorical Scale of Glabellar Line Severity at maximum frown at Month 1. [REDACTED]

[REDACTED] improvement from baseline

### 1.4.2 Secondary Efficacy Endpoints

Effective date: 2019-04-24 19:40

*Effective*

Version: 2.0

## 1.5 Safety Assessments

The methods for collecting safety data are described in Section 7.2 of the Clinical Study Protocol.

## 1.6 Safety Endpoints

Safety endpoints include:

### (i) Treatment Emergent Adverse Events (TEAEs)

Adverse events (AEs) are to be monitored throughout the course of the study. The study period for the purpose of AE collection is defined as the period from the signing of a study specific informed consent to study exit for a subject. AEs recorded on the electronic case report forms (eCRFs) will be coded using the Medical Dictionary for Regulatory Activities (MedDRA). AEs will be classified as treatment-emergent adverse events (TEAEs) if the AE had an onset time greater than or equal to the time of the dose of study treatment.

Adverse events endpoints include:

- Incidence,
- Causality (related/not related to investigational product),
- Intensity (mild/moderate/severe),
- Time to onset,
- Duration,
- Leading to study withdrawal,
- Seriousness.

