7.2.2 Focused Physical Examination

Investigator or designee will perform a physical examination of the subject that includes the face, head, and neck. Further details are provided in Appendix 4.

[REDACTED]

The Investigator may choose to investigate any other sign that he/she observes during the physical examination and should assess all abnormal findings for clinical significance.

Clinically significant abnormal findings at the screening visit and baseline visits are exclusionary, and the subject should not be enrolled in the study. If the abnormality is not clinically significant, capture it as medical history.

For any clinically significant changes from the baseline visit, an AE is to be recorded.

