7.2.3 Vital Signs

Vital signs will be evaluated at the baseline visit (pre and post-treatment), and at each study visit

[REDACTED]

Vital signs will include blood pressure, heart rate, and respiratory rate. The subject should be in a seated position and resting for at least 10 minutes prior to taking vital sign measurements. Vital signs are to be taken prior to any blood draw, excluding baseline post-treatment measurements.

All abnormal values at the screening visit identified as clinically significant by the Investigator, will be recorded in the medical history.

For any clinically significant changes from the screening visit, an AE is to be recorded.

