7.2.6.1 Definitions

7.2.6.1.1 *Adverse Events (AE)*

According to ICH E2A, an AE is any untoward medical occurrence in a patient or a clinical investigation subject administered a pharmaceutical product and which does not necessarily have a causal relationship with this treatment. An AE can therefore be any unfavorable and unintended sign (including an abnormal laboratory finding), symptom, or disease temporally associated with the use of a medicinal (investigational) product, whether or not related to the medicinal (investigational) product.

Thus any new sign, symptom or disease, or any clinically significant worsening of an existing sign, symptom or disease (including new episodes of a chronic disease [e.g., hay fever, allergy]) compared to the condition at the first visit, should be considered as an AE. Lack of efficacy is not considered as an AE.

Notes:

- There should be an attempt to report a diagnosis rather than the signs, symptoms or abnormal laboratory values associated with the report of an AE. However, a diagnosis should be reported only if, in the investigator's judgment, it is relatively certain. Otherwise, symptoms, signs, or laboratory values should be used to describe the AE.
- Pregnancy is not to be considered as an AE; however, is an important medical event that must be monitored as described in Section 7.2.6.2.3.

7.2.6.1.2 *Treatment Emergent Adverse Event (TEAE)*

A TEAE is an event that emerges during treatment, having been absent pre-treatment, or worsens relative to the pretreatment state.

Investigators are responsible for monitoring, recording, and reporting all AEs that occur during the study as described. TEAEs will be delineated from AEs following database lock.

7.2.6.1.3 *Serious Adverse Events (SAE)*

A SAE is any untoward medical occurrence that at any dose:

- Results in death,
- Is life-threatening,
- Requires inpatient hospitalization or prolongation of existing hospitalization,

- Results in persistent or significant disability/incapacity, or
- Is a congenital anomaly/birth defect.

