7.2.6.2 Reporting Procedures

7.2.6.2.1 Procedures for Reporting Adverse Events

The collection of AEs is from the time that a subject signs the ICF to their final visit.

At each post-enrollment visit, the Investigator (or sub-Investigator) will question the subject about AEs using an open non-persuasive question to elicit reporting of AEs, for example “Have you noticed any change in your health since the last visit?” Directed questioning and examination will then be performed as appropriate.

Any AE occurring during the AE reporting period, whether it is related to the study product or not, will be recorded immediately in the source document, and described on the AE form of the eCRF along with the date of onset, severity, relationship to the study product, and outcome, without omitting any requested and known information. Additional information will be requested under certain circumstances.

Adverse Events (AEs) assessed as related to the treatment or study procedure will be monitored until they have resolved or reached a stable condition. Other AEs will be monitored until the last visit if they have not resolved or reached a stable condition.

The Investigator will obtain and maintain in the subject’s files all pertinent medical records, information and medical judgment from colleagues who assisted in the treatment and follow-up of the subject. If necessary, the Investigator will contact the subject’s personal physician or hospital staff to obtain further details.

For SAEs (see Section 7.2.6.2.2) and pregnancies (see Section 7.2.6.2.3), the Sponsor is to be informed immediately by e-mail. The event must be reported by e-mail to the Safety Mailbox within 24 hours of receipt of the information (contact details in Section 7.2.6.2.2).

7.2.6.2.2 *Procedure for Reporting a Serious Adverse Event*

For a SAE occurring during the period of the clinical study, regardless of whether it is related to the treatment or not, and of whether it is expected or not, the Investigator must do the following:

1. Take prompt and appropriate medical action, if necessary. The safety of the subject is the first priority.
2. Ensure that the event is classified as an SAE (Section 7.2.6.1.3).
3. Complete the AE form provided in the eCRF as fully as possible.

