**(iii) Laboratory Safety Tests**

Hematology and blood chemistry laboratory safety tests will be performed [REDACTED]

Laboratory safety test endpoints include:

- Values,
- Changes from baseline.

For each out of range laboratory result, the Investigator or designee will assess for clinical significance. All clinically significant out-of-range laboratory values for blood samples collected at baseline will be recorded in the medical history. All clinically significant out-of-range laboratory values for blood samples collected after baseline are to be reported as an AE if this abnormality was not present at the baseline visit or is assessed as having worsened since the baseline visit (i.e. there is a significant change from baseline). In instances when a laboratory abnormality is reported, the Investigator is to provide a diagnosis rather than reporting individual laboratory abnormalities, whenever possible.

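### Minor, descriptive safety only: the SAP defines a TEAE by onset alone, so an AE that starts before injection and worsens afterwards on the same record counts under the protocol but not under the SAP

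*SAP*

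**What the plan says.** Protocol 7.2.6.1.2 gives two routes to TEAE status: "A TEAE is an event that emerges during treatment, having been absent pre-treatment, or worsens relative to the pretreatment state". SAP 1.6(i) gives one. An AE is treatment-emergent "if the AE had an onset time greater than or equal to the time of the dose of study treatment", and nothing in the readable SAP adds worsening. Both documents collect AEs from the signing of consent, so AEs with onset before injection can be on file.

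Several rules narrow the difference. Protocol 7.2.6.1.1 treats as an AE "any clinically significant worsening of an existing sign, symptom or disease", judged against the subject's condition at the first visit. Protocol 7.2.2 says of the physical examination: "For any clinically significant changes from the baseline visit, an AE is to be recorded". Protocol 7.2.3 says of vital signs, and SAP 1.6(v) repeats: "For any clinically significant changes from the screening visit, an AE is to be recorded". A clinically significant out-of-range laboratory value after baseline becomes an AE if it was absent at baseline or "is assessed as having worsened since the baseline visit" (SAP 1.6(iii), matching Protocol 7.2.4). SAP 1.5 relies on the protocol for collection: "The methods for collecting safety data are described in Section 7.2 of the Clinical Study Protocol".

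On the record itself, Protocol 7.2.6.2.1 has each AE described on the AE form "along with the date of onset, severity, relationship to the study product, and outcome". The readable text does not say whether worsening of an AE already on file opens a new record.

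**The concern.** Two definitions of the same endpoint are in force, and one event can be treatment-emergent under the first and not under the second. Incidence and severity of TEAEs heads the list of safety endpoints in Protocol 2.1.3. An AE caught in the gap would drop out of every TEAE table in SAP 2.5.2, including those by maximum intensity, causality, seriousness and discontinuation. It would remain in the overall AE line and the listings. Worsening after injection is also what a safety comparison with placebo is meant to show.

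The precedence rule in SAP 2.1 does not clearly settle the matter. It places the SAP above the protocol's statistical sections, whereas the TEAE definition sits in Protocol 7.2, under safety assessment. Timing matters too: Protocol 7.2.6.1.2 separates TEAEs from other AEs after database lock, so the information needed to recognise worsening has to be on the record before then.

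**Working it through.** The plan gives no figure to reproduce. The check is to run the possible cases through both definitions.

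| Case | Protocol 7.2.6.1.2 | SAP 1.6(i) |
|---|---|---|
| New event after injection | TEAE | TEAE |
| Medical-history condition, clinically significant worsening after injection (its own AE under 7.2.6.1.1) | TEAE | TEAE |
| Clinically significant worsening of a laboratory, vital-sign or examination finding after injection, recorded as its own AE | TEAE | TEAE |
| AE starts between consent and injection, does not worsen | Not a TEAE | Not a TEAE |
| AE starts between consent and injection, worsens after injection, new record opened | TEAE | TEAE (the new record) |
| AE starts between consent and injection, worsens after injection, same record kept | TEAE | Not a TEAE |

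Only the last row differs. The general rule in Protocol 7.2.6.1.1 does not clearly remove it. Its reference point is the first visit, and an AE that began after that visit is already a departure from that state. Whether its later worsening is a second AE is left open.

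**Size.** The documents give no rate for any step, so every probability below is an assumption. The group size of 80 is from Protocol 5.1 and 9.2.

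Expected AEs affected per group = 80 × P(AE starts between consent and injection) × P(still ongoing at dosing) × P(worsens on the same record).

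- Low: 80 × 0.02 × 0.3 × 0.05 = 0.024
- Central: 80 × 0.05 × 0.5 × 0.2 = 0.4
- High: 80 × 0.10 × 0.5 × 0.4 = 1.6

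The count of subjects with at least one TEAE changes only if the subject has no other TEAE. With that probability set at 0.5, 0.65 and 0.8:

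- Low: 0.024 × 0.5 = 0.012 subjects
- Central: 0.4 × 0.65 = 0.26 subjects, and 0.26 / 80 = 0.3 percentage points
- High: 1.6 × 0.8 = 1.28 subjects, and 1.28 / 80 = 1.6 percentage points

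**Duration of related AEs (secondary).** SAP 2.5.2 calculates no duration when the stop date is missing, and does not separate ongoing events from resolved events with an unknown date. Protocol 7.2.6.2.1 allows follow-up of a related AE to end once it is stable, so an unresolved one may have no stop date. The same section of the SAP tabulates treatment-related TEAEs by treatment group, SOC and PT with event counts, so such TEAEs are still counted there. They also appear in the listings (SAP 2.1.2).

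**The case against.** The strongest reply is that the documents already close the gap. Clinically significant worsening is an AE under the general definition and again under the domain rules, and SAP 1.5 adopts those collection rules. If sites open a new record each time, onset falls after dosing and the two definitions agree. This stands for medical-history conditions and for findings recorded under the domain rules. It does not clearly stand for an AE already on file before injection, because the reference point is the first visit and the recording practice is not stated.

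It is also fair that the fields named in Protocol 7.2.6.2.1 are not a full form specification. The section says further information may be requested in some circumstances, so the eCRF may already capture a dated change in severity. Even so, the SAP rule as written would not use it.

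Stronger readings are tempting, and the documents do not support them:

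- A reader might infer an undeclared departure from the protocol. SAP 2.9, on changes from the planned analysis, is listed in the contents but not readable, so this cannot be said.
- A reader might infer that TEAEs are undercounted in general. Five of the six cases above agree.
- A reader might infer that related AEs without a stop date vanish, or that reported durations are biased in a known direction. TEAEs without a stop date remain in the related-TEAE tables, and all such AEs remain in the listings. Protocol 7.2.6.2.1 caps follow-up at the last visit only for AEs not assessed as related. The table formats are in a companion document not available here, which may already show the number without a duration. Leaving out ongoing events shortens the summary. Leaving out short events with an unknown stop date, or setting a missing start to the treatment day, can lengthen it. The net direction is unknown.

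**Conclusion.** The point holds in a narrow form and is minor. The two definitions disagree for one kind of event: an AE that begins between consent and injection and worsens after dosing without a new record. The number affected cannot be determined from the documents and is probably very small. The illustrative range of 0.02 to 1.6 AEs per 80-subject group rests wholly on assumed rates. SAP 2.5 plans no inferential analysis of safety, so no test or efficacy conclusion depends on it. It is worth correcting because it concerns the definition of the first-listed safety endpoint and the correction is cheap. The duration item is a reporting clarification and not an error.

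**What to change.** Align SAP 1.6(i) with the protocol by adding, after the onset condition: *or began before dosing and worsened after dosing relative to the pre-treatment state*. Worsening is a better term than an increase in intensity, which would be narrower than the protocol's definition.

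Before database lock, choose one recording method and put it in the eCRF completion instructions: either a new AE record at the time of worsening, or a dated worsening on the existing record. Only one should be used. If both were in play, the same event could be counted twice.

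If the narrower SAP definition is intended, say so and reconcile it with Protocol 7.2.6.1.2.

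The cost is one phrase in the SAP, one completion rule, and a few queries limited to AEs with onset between consent and injection. TEAE counts may rise slightly. Under the same-record option, time to onset for such an AE would have to run from the worsening date, because the SAP 2.5.2 formula (start date minus treatment date) would give a negative value.

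Optionally, footnote the related-AE duration summary with the number of related AEs without a calculated duration, by treatment group, split into ongoing and unknown stop date. SAP 2.1.2 allows changes to table formats without an amendment, so this costs little more than one count.
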